9.7. Data analysis

All data analyses will be performed by Dendrite Clinical Systems together with Nordic after the Key Data are completed. Statistical programming and analyses will be performed using SAS and/or other statistical software as required.

Analysed data will be reviewed by an Independent Data Safety Monitoring Committee, involving at least four (4) national coordinating investigators.

The Registry will collect information for all patients who receive Nordic Aprotinin for any purpose in participating countries in Europe. The Registry will not allow a direct comparison of mortality and morbidity among patients treated with aprotinin to patients not with aprotinin. Mortality and morbidity outcomes vary according to patient selection criteria by centre and by country of treatment. Historical controls are not wholly reliable as patient selection and operative techniques vary over time. It is proposed to examine external data bases for comparative purposes as these may be used as a yardstick to measure patient outcomes, e.g. reports from existing national or European cardiac surgical databases. These external data will be mentioned in the Statistical Analysis Plan (SAP) prior to the first analysis.

The analysis of data from the Registry will be descriptive, and all information will be reported in summary tables.

The intention is to focus on those variables most pertinent to assessing compliance with approved labelling, including compliance with the approved indication, and compliance with instructions for appropriate use, including use of heparin and monitoring of anticoagulation. Summary data will be provided for all variables collected and the data will be reported overall, by country, and if required by centre.

The first data analyses will be conducted six months after the completion of data entry of the first subject in the study depending on PSUR scheme and timelines and will be repeated six months later. Thereafter the analyses will be conducted annually until the close of the Registry (i.e. for at least three years). Overall reports will be synchronised between each country so that **the analyses are all conducted at the same time.**

Analysis will be made of the data for Nordic Aprotinin overall, by individual country and if required by individual site. The analysis will include the following key outcomes and variables will be presented:

The outcomes to be included in each report will include at least:

- Death
- Myocardial infarction (fatal and non-fatal)
- Renal failure (fatal and non-fatal)
- Renal failure with and without aminoglycoside use

- Stroke (fatal and non-fatal)
- Other embolic or thrombotic event (fatal and non-fatal)
- Blood loss: requiring blood product transfusion, requiring re-operation
- Blood product transfusion
- Anaphylaxis

Note: allergic reactions and anaphylactic/anaphylactoid reactions are rare (between 1/10,000 and 1/1,000) and anaphylactic shocks are very rare (below 1/10,000) when appropriate preventative measures are taken so none may be reported. If any occur the details will be reported separately.

Variables included in the analysis:

Analysis of each outcome will be presented by: country, age categories, sex, presence of anti-platelet agents active at time of operation, cardiac by-pass and operative type (on label and off-label). Other variables may be included as considered appropriate by an Independent Data Safety Monitoring Committee or as requested by the PRAC.

The final analysis will be based on the population entered at three years following completion of the first patient. The analysis will include at least the information above and will include further analyses as suggested by the results and as requested by the Competent Authorities concerned and the Independent Data Safety Monitoring Committee (IDSMC).

A review will be conducted by the IDSMC every six months throughout the study. The results of the six months initial interim report and of each annual report will be available in full to the PRAC to allow full review for safety signals. Previous mortality and morbidity data from existing cardiac surgery databases will be available as a yardstick. This may occur when a potential safety signal arises. Outcome data between different participating centres within the Registry may also be analysed when appropriate.

Additional analyses can be made available on a flexible basis depending on the outcomes in the study. In addition to the above further analyses may be undertaken when appropriate according to the ongoing findings from the Registry and as requested by the PRAC (and other Competent Authorities if required).

Rates and confidence intervals:

Rates and exact 95% confidence intervals will be computed for all identified adverse events and potential risks and all relevant criteria.

Missing data:

As a matter of fact imputation of data is more or less invention of data that can strongly bias results in an observational study. The less speculative approach is therefore to remove from the data patients without the needed information from the analysis.

In data modelling or if a breakdown of the sample is done according a given variable, a missing data in any qualitative covariate (or factor of segmentation of the sample) can have a category called "unknown". A first model will fitted with such a categorization and a second one will be fitted after removing all patients with missing data on the covariate. If it concerns a breakdown of the sample then descriptive statistics along with 95% confidence interval will be provided for all categories including the unknown class. Regarding quantitative covariate, categorization of the covariate may be done and a first model will be fitted with only categorical variables including the "unknown" category and a

second model is fitted with quantitative covariate (patients with a missing data are excluded). Concerning the breakdown the same categorization approach will be applied and estimation will be provided for each category. If a breakdown of the sample is applied the estimation for the "unknown" category will be compared to all the other categories combined to assess whether missing data represent approximately the average of the collected data.

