Data analysis	
All data analyses will be performed by Dendrite Clinical Systems together with Nordic after the Key Data are completed. Analysed data will be reviewed by an Independent Data Safety Monitoring Committee, involving at least four (4) national coordinating investigators.
 
The analysis of data from the Registry will be descriptive, and all information will be reported in summary tables. Summary data will be provided for all variables collected and the data will be reported overall, by country, and if required by centre. The intention is to focus on those variables most pertinent to assessing compliance with approved labelling and instructions for appropriate use, including use of heparin and monitoring of anticoagulation. The data will also be reviewed for any safety signals. The outcomes to be included in each report will include at least: death, myocardial infarction, renal failure with and without aminoglycoside use, stroke and other embolic or thrombotic event, blood loss (requiring transfusion, requiring re-operation), blood product transfusion and anaphylaxis.
 
Analysis of each outcome will be presented by: country, age categories, sex, presence of anti-platelet agents active at time of operation, cardiac by-pass and operative type. Other variables may be included as considered appropriate by an Independent Data Safety Monitoring Committee or as requested by the PRAC.
 
Overall reports will be synchronised with PSUR scheme and timelines.

Planned milestones	
Study start: planned for Q2 2015
 
Recruitment completed: when a maximum of 5,268 patients will be included (estimated in January 2020). This number of patients should be enough to obtain 3,951 analysable patients.
 
Interim statistical reports: every 6 months after launch.
 
Interim medical report: every 2 years with PSUR.
 
Last data collection: when a maximum of 5,268 patients will be included (estimated in January 2020). This number of patients should be enough to obtain 3,951 analysable patients.
 
Final study report: 12 months after the end of Data collection (prospective collection). The Registry will operate for at least three years beginning with Nordic Aprotinin's return to the market in Europe, and the decision to terminate the Registry will be taken based on agreement with the PRAC.

5. Amendments and updates

Number	Date	Section of the study protocol	Amendment or update	Reason
Version 1.0			submitted 17 September 2014	

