9.3.2. Operation *

Type of operation elective, urgent, emergency or salvage;
If urgent the reason for urgency;
The number of previous heart operations;
Type of procedure (including valve surgery).

Other surgical procedures will be detailed if relevant. *Note: If the indication for using aprotinin is entirely within the authorised indication up to and at the time of aprotinin administration but complications or unforeseen circumstances arise during surgery and the concerned patient requires further surgery the patient will be considered as an “unintended off-label” case.*

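### Section 9.7 does not clearly commit to outcomes by urgency of operation, so crude on-label/off-label and country differences may partly reflect urgency mix

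*Protocol*

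**What the plan says.** Section 9.7 introduces the outcomes with "The outcomes to be included in each report will include at least"; death comes first, and myocardial infarction, renal failure and stroke are also listed. Each outcome is then to be broken down by country, age category, sex, anti-platelet agents, "cardiac by-pass and operative type (on label and off-label". The abstract (section 4, data analysis row) repeats the list as "presence of anti-platelet agents active at time of operation, cardiac by-pass and operative type", with nothing in brackets.

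Section 9.3.2, one of the Key Data pages, records two different things that could be called operative type: "Type of operation elective, urgent, emergency or salvage", and separately "Type of procedure (including valve surgery", a parenthesis that closes there. Section 9.3 makes Key Data the minimum required for each patient.

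On the kind of analysis, section 9.7 says "The analysis of data from the Registry will be descriptive, and all information will be reported in summary tables", and "Summary data will be provided for all variables collected and the data will be reported overall, by country, and if required by centre". It also warns that "Mortality and morbidity outcomes vary according to patient selection criteria by centre and by country of treatment". Further variables may be added if the monitoring committee considers them appropriate or the PRAC asks for them.

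**The concern.** Label status does not stand in for urgency. The indication set out in Annex 1 (the DHPC) turns on adult age, high bleeding risk and isolated bypass graft surgery, and does not mention urgency. On-label and off-label groups can therefore contain different shares of emergency and salvage operations, and so can countries. If mortality is higher in those operations, the crude rates will differ even where label status and country have no effect.

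The tables will be read for safety. Section 9.7 provides for six-monthly committee review and gives the PRAC the results to look for safety signals. Section 11.2.1 looks for patterns of concern at country and centre level. Off-label use is listed as missing information in Table 1 (section 8.3). A high crude off-label death rate could be taken for a hazard, or a low on-label rate for reassurance, with no planned table to show whether urgency explains it.

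**Working it through.** **What is and is not committed**

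- Outcome by label status and by country: committed in 9.7.
- Distribution of urgency, overall and by country: covered by the general promise to summarise all variables.
- Outcome by urgency: not named in 9.7, unless 'operative type' is taken to mean urgency.
- Urgency by label status: not named anywhere in the protocol.

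**The plan's own figure.** No figure in the plan bears directly on this point. The study size, used below for precision, reproduces. A 95% interval with margin 1.56% at 50% needs 1.96² × 0.25 / 0.0156² ≈ 3,947, against 3,951 stated, and 3,951 / 0.75 = 5,268. An added breakdown changes neither number.

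**How far urgency mix alone could move a crude ratio.** The documents give neither the urgency mix nor mortality by urgency, so all inputs here are assumptions. Let e be the share of emergency or salvage cases in a group, m0 the mortality in other cases and m1 the mortality in emergency or salvage cases. Take m0 and m1 to be the same on and off label, so there is no true label effect.

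Crude rate = (1 − e) × m0 + e × m1

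With m0 = 2% and m1 = 12%:
- e = 5%: 0.95 × 2% + 0.05 × 12% = 2.5%
- e = 25%: 0.75 × 2% + 0.25 × 12% = 4.5%
- ratio 4.5 / 2.5 = 1.80

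The same formula gives:

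| Emergency share, on v off label | m0 2%, m1 12% | m0 3%, m1 15% |
|---|---|---|
| 10% v 10% | 3.0% v 3.0%, ratio 1.00 | 4.2% v 4.2%, ratio 1.00 |
| 5% v 15% | 2.5% v 3.5%, ratio 1.40 | 3.6% v 4.8%, ratio 1.33 |
| 5% v 25% | 2.5% v 4.5%, ratio 1.80 | 3.6% v 6.0%, ratio 1.67 |
| 10% v 30% | 3.0% v 5.0%, ratio 1.67 | 4.2% v 6.6%, ratio 1.57 |
| 25% v 5% (reversed) | 4.5% v 2.5%, ratio 0.56 | 6.0% v 3.6%, ratio 0.60 |

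So the direction as well as the size depends on a mix that the documents do not give.

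**Could this look like a signal at the planned size?** Take 3%/15% mortality, shares of 5% v 25%, and 3,951 patients split in half (also assumed). The expected deaths are about 71 of 1,976 and 118 of 1,975. The exact 95% intervals are 2.8% to 4.5% and 5.0% to 7.1%. They do not overlap, although no label effect was assumed.

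**Is the extra breakdown feasible?** If emergency and salvage cases make up 5% to 30% of 3,951, that stratum holds 198 to 1,185 patients. At 15% mortality the 95% half-width, 1.96 × √(0.15 × 0.85 / n), is about 5.0 points at n = 198 and 2.0 points at n = 1,185. That is usable overall, but thinner once crossed with country.

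**The case against.** The strongest reply is that the bracket in 9.7 can be read the other way, as operative type shown for both on-label and off-label operations. With the unbracketed abstract, and with type of operation meaning urgency in 9.3.2, urgency would then already be a listed breakdown. That reading is possible. It is why the point is partly one of definition, and why a reader should not infer that the plan deliberately excludes urgency.

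The list is also a minimum. The committee or the PRAC may add variables, the missing-data text in 9.7 allows for covariate models, and the SAP, which is not shown, may specify urgency. These routes are real, but in the protocol they are discretionary, and 9.7 ties some further analyses to what the results suggest. A stratifier chosen after a signal appears is weaker than one fixed beforehand. The inconsistent term needs correcting whatever the SAP says.

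The analysis is descriptive, no objective in 8.2 or 8.3 compares on-label with off-label mortality, 8.1 disclaims a quantitative benefit-risk assessment, and the case-mix warning is explicit. All of this stands and limits the weight of the point. A warning does not, however, let a reader see how much of a difference urgency accounts for.

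Finally, urgency is only one case-mix factor. Procedure type and previous heart operations, also recorded in 9.3.2, may differ by label status too, so stratifying by urgency alone would not make the groups comparable. That stands, and the fix should say so.

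**Conclusion.** The point holds in a limited form. 'Operative type' is used inconsistently across the abstract, 9.3.2 and 9.7. On the natural reading of 9.7, neither outcome by urgency nor urgency by label status is a committed table. Crude label and country differences may therefore partly reflect urgency mix.

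A reader might go further and infer that these differences do reflect the emergency mix. The documents do not support that, because nothing in them shows that urgency differs by label status or by country.

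The size is unknown. Under the assumed mortalities the spurious off-label to on-label ratio is 1.00 with equal emergency shares, 1.33 to 1.80 in the scenarios with more emergencies off label, and below 1 in the reverse case. This is a cheap improvement to a descriptive plan, not a flaw that undermines the registry's objectives.

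**What to change.** In 9.7 and in the abstract, replace 'operative type' with two separately named breakdowns: label status, and urgency of operation as recorded in 9.3.2. Show the main outcomes by label status and by country within urgency strata, combining emergency and salvage if sparse, or directly standardised to the registry's overall urgency mix. Carry an 'unknown' urgency class, as the missing-data text in 9.7 already allows for breakdowns. State beside these tables that other case-mix differences, such as procedure type and previous heart operations, remain.

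The cost is a few more table rows and some sparse cells, chiefly salvage cases and small countries. No new data item is needed and the study size is unchanged. Urgency may not be complete for every patient: 9.3 expects some incomplete Key Data, and the rationale in section 5 refers to a completeness target of above 80%.

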
during the study period
	
...
 
The final study report (data collected prospectively only) will be submitted within 6 months following the completion of the study. If this is delayed for any reason the reasons for the delay will be communicated. The planned publication will conform to STROBE guidelines (cf. References).
	
...
 
The final study report (data collected prospectively only) will be submitted within 12 months following the completion of the study. If this is delayed for any reason the reasons for the delay will be communicated. The planned publication will conform to STROBE guidelines (cf. References).
	
--------------------------------	---	--	--

6. Milestones

Table with planned dates for the following milestones:

Milestone	Planned date	Rationale
Start of data collection	February 2016	At the launch of Nordic Aprotinin in the first participating country (i.e. Aprotinin 10,000 KIU/ml Injection BP in the UK)
End of data collection	when a maximum of 5,268 patients will be included (estimated in January 2020).	This number of patients should be enough to obtain 3,951 analysable patients.
Study progress reports and Interim reports of study results 1	17 May 2018 (with PSUR report)	Clinical study report are done following the same timelines and scheme as PSUR. Bi-annual statistical reports are done for DSMC review
Study progress reports and Interim reports of study results 2	28 May 2020 (with PSUR report)	
Registration in the EU PAS register	8 February 2019	Last update
Final report of study results	Estimated December 2020	The final report of study results (data collected prospectively only) will be made available twelve months after the last patient included

7. Rationale and background

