8.1. Aim of the Study

The aim of the Registry is to collect information over time on the pattern of use of Nordic Aprotinin and to record the proportion of patients exposed to aprotinin in accordance with the authorized indication in participating European countries during the three year period beginning from the day that Nordic Aprotinin becomes available to the market. To have access to Nordic Aprotinin and to become a participating centre, centres have to perform cardiac surgery on cardio-pulmonary bypass and to commit to enrol in the Registry (as described in Annex 4). Thus, it is expected that virtually all patients who receive Nordic Aprotinin at all participating cardiac surgery centre in participating countries in Europe will be included in the Registry. The Registry will provide information on the number of patients who receive Nordic Aprotinin by centre, the recorded indication (surgical procedure, features of the indication), the characteristics, including risk factors and the conditions of use, including adherence to instructions for administration in the approved SmPC. The Registry will also collect additional information from healthcare professionals relevant to patient characteristics that may be related to the decision to use Nordic Aprotinin. Information from the proposed Registry will provide a profile over time of Nordic Aprotinin utilization in participating countries following return to the market.

It is proposed to collect similar information on any patients who are given Nordic Aprotinin within or outside its licensed indications, to allow the assessment of off-label use as part of the missing information, as required in the CHMP assessment report (EMA/590581/2013). **Data collection**

regarding off-label use will be done in accordance with national legal frameworks and will be discussed with the national competent authority prior to launch if necessary and adapted accordingly.

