9.5. Study size

All patients exposed to Nordic Aprotinin, at all participating cardiac surgical centres in European countries with marketing authorisation, are intended to be included during the study.

The study is designed primarily to monitor the pattern of use and record utilisation information such as the proportion of patients exposed to aprotinin in accordance with the authorized indication.

Considering that the registry of Great Britain & Ireland recorded just over 400,000 operations in 5 years and that the US one collected around 280,000 operations/year^{15,16}, we could postulate that, across Europe, at least 300,000 patients are undergoing cardiac surgery.

Thus, we estimate the sample size based on the occurrence of events of specific interest (such as type of procedure, death, thromboembolic, stroke ...) with a reasonable precision.

To obtain 95% confidence interval with a maximum margin error of 1.56%, 3,951 patients should be included. This margin error is the maximum one that can be obtained: it is the one based on the assumption that an event of interest is observed in 50% of patients (meaning a 95% CI of [48.44% ; 51.56%]). In all other cases (i.e. event of interest observed in less or more than 50%), precision will only be better (less than 1.56%).

There is no a priori calculation of power for this study because the main primary objective is descriptive rather than inferential and because the adverse event included in the other primary objectives such as in-hospital mortality, thromboembolic events or renal dysfunction are dependant of aprotinin's pattern of use.

Taking into account an exclusion rate of 25% (patient refusing data collection, un-exposed to aprotinin in the course of cardiac surgery with CPB, or undergoing off pump surgery), the number of patients to include is 5,268.

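### Section 9.7 closes the final-analysis population three years after the first patient, which conflicts with the count-based end of data collection in section 6 and the sample size in 9.5

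*Protocol*

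**What the plan says.** - **Protocol 9.7 (Data analysis)** defines the final population by time: "The final analysis will be based on the population entered at three years following completion of the first patient".
- **Protocol 6 (Milestones)** gives the start as "Start of data collection February 2016" and ends data collection by count: "when a maximum of 5,268 patients will be included (estimated in January 2020". The rationale beside it reads "This number of patients should be enough to obtain 3,951 analysable patients". The final report is timed from the end of inclusion: "The final report of study results (data collected prospectively only) will be made available twelve months after the last patient included".
- **Protocol 4 (Abstract)** repeats the 5,268 and 3,951 figures for both completed recruitment and last data collection.
- **Protocol 9.5 (Study size)** bases precision on the analysable number: "To obtain 95% confidence interval with a maximum margin error of 1.56%, 3,951 patients should be included". It gives no calendar date and no separate rule for the final analysis.
- **Protocol 8.1 (Aim)** describes the proportion treated within the indication as recorded "during the three year period beginning from the day that Nordic Aprotinin becomes available to the market".
- **Protocol 9.1, 9.2 and 12.2** treat three years as the minimum running time of the Registry.

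**The concern.** Two rules bear on who is in the final analysis, and they do not select the same patients. One closes at a fixed time after the first patient. The other lets inclusion continue to a target count, and the stated precision rests on that count. A minimum duration of three years does not reconcile them, because the 9.7 sentence sets a population at three years and not at registry close.

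The population supplies the denominators and the calendar period for every primary objective: use within the indication, death, thromboembolic events, renal dysfunction and anaphylaxis. In 12.3 the sponsor undertakes to report strictly according to the protocol and the SAP, so a literal reading of 9.7 has consequences. It would set aside patients whom section 6 collected in order to reach the planned size, and the margin in 9.5 would not be achieved.

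**Working it through.** **Inputs from the protocol**
- Start of data collection: February 2016 (section 6, in the planned-date column).
- End of data collection: 5,268 included, estimated January 2020 (section 6, abstract).
- Analysable number 3,951 and margin 1.56% at an assumed proportion of 50% (9.5: "it is the one based on the assumption that an event of interest is observed in 50% of patients"); exclusion rate 25% (9.5).
- For the date arithmetic only, 7 January 2020 is taken as the end point. It is the extraction at which, according to the change table in section 5, 3,951 analysable patients were available.

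**Reproducing the plan's own figures**
- n = (1.96 × 0.5 / 0.0156)² = 3,947, against 3,951 stated.
- Margin at 3,951: 1.96 × √(0.25 / 3,951) = 1.559%.
- Number to include: 3,951 / (1 − 0.25) = 5,268.

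The sample-size arithmetic is sound.

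**Length of the gap**
- February 2016 to 7 January 2020 is 47.2 months from 1 February, or 46.3 months from 29 February.
- The 9.7 rule closes at 36 + L months, where L is the lag from the start of collection to completion of the first patient. The protocol does not state L, so 0 to 6 months is assumed.
- L = 0: 47.2 − 36 = 11.2 months left out. L = 6: 47.2 − 42 = 5.2 months left out.

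**Patients left out**

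The protocol gives no accrual by date, so two patterns are assumed:
- uniform accrual: kept = 3,951 × (36 + L) / 47.2
- linearly rising accrual rate: kept = 3,951 × [(36 + L) / 47.2]²

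The worst-case margin is 1.96 × √(0.25 / kept).

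| Accrual | L (months) | Kept | Left out | Margin |
|---|---|---|---|---|
| Uniform | 0 | 3,015 | 936 | 1.78% |
| Uniform | 3 | 3,266 | 685 | 1.71% |
| Uniform | 6 | 3,517 | 434 | 1.65% |
| Rising | 0 | 2,298 | 1,653 | 2.04% |
| Rising | 3 | 2,697 | 1,254 | 1.89% |
| Rising | 6 | 3,128 | 823 | 1.75% |

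The loss runs from 434 / 3,951 = 11% to 1,653 / 3,951 = 42%. None of these cases meets the 1.56% margin.

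**Sensitivity to the start date**

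The abstract still shows a planned start in Q2 2015. From that date the end point is 54.3 to 57.2 months away, and the gap at L = 0 is 18.3 to 21.2 months. Uniform accrual would then keep 2,485 to 2,621 patients. The table uses the section 6 date, which gives the smaller conflict.

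**The case against.** The best defence is that the intent can be read from the rest of the protocol. Three years is a minimum almost everywhere else. Section 9.7 itself says that periodic analyses continue until the Registry closes. Section 6 times the report from the last patient. The sentence in 9.7 looks like a remnant of the earlier three-year design, since the change table lists revisions to sections 6 and 9.5 but none to 9.7. A careful reader would probably apply the count-based rule. This lowers the urgency, but it does not make the sentence correct.

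Several limits on the point stand:
- Section 9.5 supplies only numbers. January 2020 is an estimate from section 6 and the abstract, and early 2019 is derived.
- Any single figure for months or patients lost depends on accrual and lag assumptions that the protocol does not settle.
- The loss of precision is modest. At an illustrative event proportion of 5%, the margin 1.96 × √(0.05 × 0.95 / n) goes from 0.68% at 3,951 to between 0.72% (n = 3,517) and 0.89% (n = 2,298).
- A SAP dated 23 September 2019 is listed in Annex 1 but not shown, and it may define the analysis set. It would not remove the contradiction within the protocol.

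A reader might also infer that, with six-monthly reviews under way, the cut-off could be chosen after the outcome tables were seen. The documents do not support that. The analysis is descriptive and has no comparator, the count-based rule is written down in several places, and nothing shows a cut chosen from results.

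**Conclusion.** The 9.7 sentence is wrong as written and needs aligning with the rest of the protocol. Read literally, it excludes patients entered after about early 2019, whereas section 6 and the abstract collect to an estimated January 2020 and the margin in 9.5 depends on that full count. The gap is roughly 5 to 11 months, if collection began in February 2016 and the first patient was completed within six months. Under uniform to linearly rising accrual, about 430 to 1,650 of 3,951 analysable patients (11% to 42%) would be left out, with a worst-case margin of about 1.65% to 2.04%.

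The contradiction does not depend on the accrual pattern, but its size does. The upper end of the range should not be quoted as the expected loss, because it needs an accrual rate rising from zero and no first-patient lag. The finding is an unreconciled definition. It is not evidence of a biased analysis or of an error in the sample size.

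**What to change.** Replace the 9.7 sentence with wording such as: *The final analysis population comprises every analysable patient, in the sense of section 9.5, entered between the first patient and the end of data collection set in section 6.* In 8.1, change the fixed three-year period to *at least three years*, to agree with 9.1, 9.2 and 12.2.

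Two choices of wording matter:
- Refer to the end of data collection in section 6 and do not write in the 7 January 2020 extraction date. That date appears only in the change table, and no current section calls it the data lock.
- Refer to analysable patients and not to all exposed patients. The 3,951 in 9.5 is what remains after refusals, unexposed patients and off-pump surgery are removed.

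A table of the three-year cohort may be kept as a sensitivity analysis. The cost is one sentence in 9.7 and one phrase in 8.1, with no new data and no change to the timeline.
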